9.4.1.2. Analyses for Continuous Endpoints

The non-longitudinal continuous data will be analyzed by ANOVA with treatment as the factor. ANCOVA will be used if relevant baseline value and/or other factors are included as covariates. Comparison of crisaborole ointment, 2%, BID to vehicle (providing LSM of the treatments, LSM of the treatment difference, one-sided p-value and 90% CI) will be generated.

The longitudinal continuous data will be analyzed using MMRM with fixed effects of treatment group, visit, and treatment-group by visit interaction, without imputation for missing values. If the endpoint is change from baseline, baseline will be included in the model as a covariate. A common unstructured variance-covariance matrix will be used, provided it converges. If this is a convergence issue, other type of covariance matrix such as first order autoregressive, compound symmetry will be used. Comparison of crisaborole ointment, 2%, BID to vehicle (providing LSM of the treatments, LSM of the treatment difference, one-sided p-value and 90% CI) at each time point during the first 6 weeks will be generated using this model.

9.4.1.3. Analyses for Categorical Endpoints

The frequency and percentage for each category will be presented for category endpoints.

9.4.2. Primary Endpoint/Estimand Analyses

Percent change from baseline in TSS at Week 6/EOT based on HVP in person assessments (primary analysis) will be analyzed using an ANOVA model that includes treatment group as a factor (see Section 9.4.1.2). . The primary analysis of the primary endpoint will be based on Estimand 1 using FAS.

Some supportive/sensitivity analyses and subgroup analyses may be performed for the primary endpoint. Detail will be given in the SAP.

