	Screening Visit (Home Visit)	Pre- Randomization Period	Randomization (telemedicine)	Training Visit (Home Visit)	
Day(s)	-28 to -15	-14 to -8	-7 to -2	-2 to +1	
Window (days)	±2	±2	±2	±2	
Lower extremity digital imaging	X			X	The HVP will instruct the participant how to obtain static SD lesion images at the training visit. Section 8.1.2 and Section 8.1.3
Total Sign Score (TSS)	X			X	To be completed by the HVP prior to dose administration at the training visit. Section 8.1.4.1
Investigator's Static Global Assessment (ISGA)	X			X	To be completed by the HVP prior to dose administration at the training visit. Section 8.1.4.2
Lesional % of Body Surface Area (BSA)	X			X	To be completed by HVP prior to dose administration at the training visit. Section 8.1.4.3
Patient Reported Outcomes					
CCI	[REDACTED]	[REDACTED]	[REDACTED]	[REDACTED]	[REDACTED]
	[REDACTED]	[REDACTED]	[REDACTED]	[REDACTED]	[REDACTED]
	[REDACTED]	[REDACTED]	[REDACTED]	[REDACTED]	[REDACTED]

Procedure	Screening Period				Notes
	Screening Visit (Home Visit)	Pre-Randomization Period	Randomization (telemedicine)	Training Visit (Home Visit)	
Day(s)	-28 to -15	-14 to -8	-7 to -2	-2 to +1	
Window (days)	±2	±2	±2	±2	
CCI	■				■
Safety Assessment					
Serious and non-serious AE reporting	X	X	X	X	Including AEs reported during referral clinic visits. Section 8.3
Study Intervention					
Prior and Concomitant medications / therapies recording on eCRFs	X	X	X	X	Section 6.5
eDiary 
 • Device and compatibility assessment • eDiary completion training 	X				Training and assessment provided by the HVP at the screening visit. Section 8.1.5
Home visit practitioner (HVP) demonstration 
 • Study intervention handling and dosing instruction 				X	Training visit by the HVP will occur following participant randomization and study intervention assignment. In the event that study intervention cannot be applied, HVP may use ointment without a pharmacologically active ingredient for demonstration. Section 6.1.1 and Section 6.2

Procedure	Screening Period				Notes
	Screening Visit (Home Visit)	Pre-Randomization Period	Randomization (telemedicine)	Training Visit (Home Visit)	
Day(s)	-28 to -15	-14 to -8	-7 to -2	-2 to +1	
Window (days)	±2	±2	±2	±2	
Study intervention dispensing			X		Section 6.2

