5.1. Inclusion Criteria

Participants are eligible to be included in the study only if all the following criteria apply:

Age

1. Participant must be ≥ 45 years of age at the time of signing the informed consent.

Type of Participant and Disease Characteristics

2. Participants who have SD:

- A known diagnosis of SD based upon HCP medical records for at least 3 months prior to screening with inadequate response to current treatment. Inadequate response is defined by ISGA ≥ 2 (range 0-4) and TSS ≥ 3 (range 0-12) at the screening visit;

OR

- Newly diagnosed by the Investigator based upon the following:
 - a. Participant confirmation of symptoms present on lower extremities for at least 3 months prior to screening;
 - b. HVP complete physical examination findings;
 - c. Telemedicine assessment by the Investigator;
 - d. Inadequate response to current treatment. Inadequate response is defined by ISGA ≥ 2 (range 0-4) and TSS ≥ 3 (range 0-12) at the screening visit.
- Active unilateral or bilateral SD lesions on the lower extremities (from knee to ankle and dorsum of foot) and the involved areas total $\geq 1\%$ BSA (1 handprint of the participant) at the screening visit.

Sex

3. Male or Female

Informed Consent

4. Capable of giving signed informed consent as described in [Appendix 1](#) which includes compliance with the requirements and restrictions listed in the informed consent form (ICF) and in this protocol.

Other

5. Participant's mental and physical status allows them to be able to mostly perform their activities of daily living with minimal assistance including the ability to:
 - a. Apply ointment to the lower part of their legs;
 - b. Comply with compression therapy, if worn prior to screening;
 - c. Comply with study procedures, including home visits, digital imaging and image capture;
 - d. Comply with use of an internet-enabled device, (eg smartphone, tablet, laptop or desktop computer) to complete patient-reported outcome assessments (PROs), and the dosing diary.

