9.4.3. Secondary Endpoints/Estimands Analysis

Percentage change from baseline in %BSA at Week 6/EOT based on in-person assessment will be analyzed using an ANOVA model that includes treatment group as a factor (see [Section 9.4.1.2](#)) based on Estimand 1 using FAS.

Achievement of an ISGA success and ISGA clear/almost clear at Week 6/EOT based on in-person assessment will be analyzed using the method described in [Section 9.4.1.1](#) using Estimand 1 and FAS.

Percent change from baseline in TSS and %BSA based on Central Readers assessments will be analyzed using MMRM as described in [Section 9.4.1.2](#). Missing data are assumed MAR. Under MAR assumption, MMRM will yield unbiased estimates and valid inferences for treatment effects assuming all participants maintain therapy. This analysis will be based on Estimand 3 using FAS.

Achievement of an ISGA success and ISGA clear/almost clear by time point based on Central Readers assessments will be analyzed using the method described in [Section 9.4.1.1](#). Observations after the discontinuation of study intervention or missing values for any reason will be handled by setting the endpoint to nonresponsive. Note that this is a composite endpoint in the sense that a response requires the participant completes a visit of interest eg, Week 6, and achieves a response per the defined response criteria (otherwise it is considered a nonresponse). This method of handling missing response is known as missing response as non-response (MR-NR). The analysis will be based on Estimand 2 using FAS.

CCI

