5.2. General Methods

In general, number, percent and 90% confidence interval (CI) will be presented for binary endpoints. Descriptive summary statistics (n, Mean, Standard deviation (Std), Median, Min., Max.) will be presented for continuous endpoints. In addition, graphics may be used to present the data.

Day 1 will be the date when a participant applies the first dose of study intervention. Baseline value will be the last non-missing assessment on or before Day 1 and prior to first dose of study intervention. **CCI**

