5.2.1. Analyses for Continuous Data

Analysis of Variance (ANOVA)/Analysis of Covariance (ANCOVA) for Non-longitudinal Continuous Data:

The non-longitudinal continuous data will be analyzed by ANOVA with treatment as the factor. ANCOVA will be used if relevant baseline value and/or other factors are included as covariates. Comparison of crisaborole ointment, 2%, BID to vehicle (providing LSM of the treatments, LSM of the treatment difference, 1-sided p-value and 90% CI) will be generated.

Mixed Effect Model Repeat Measurement (MMRM) for Longitudinal Continuous Data:

The longitudinal continuous endpoints will be analyzed with MMRM that includes fixed effects of treatment group, visit, and treatment-group by visit interaction, without imputation for missing values. If the endpoint is change from baseline, baseline will be included in the model as a covariate. A common unstructured variance-covariance matrix will be used, provided it converges. If this is a convergence issue, other type of covariance matrix such as first order autoregressive (AR[1]), compound symmetry will be used. Comparison of crisaborole ointment, 2%, BID to vehicle (providing least squares means [LSM] of the treatments, LSM of the treatment difference, 1-sided p-value and 90% CI) at each time point during the first 6 weeks will be generated using this model.

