6.1.2. Sensitivity Analyses

Two sensitivity analyses will be performed for the percent change from baseline in the TSS at Week 6 based on HVP in-person assessment.

1. Observed cases: Principal Stratum estimand will be used. The data after an intercurrent event discontinuation of study intervention, if collected, will be excluded, only no-missing observed cases in-person assessment at Week 6 (based on window definition in Table 3) will be included in the analysis. No imputation for missing data. ANOVA ([Section 5.2.1](#)) will be used. The LSM along with the corresponding SE for each treatment group, LSM difference along with the corresponding SE, 90% CI, and 1-sided p-value will be presented. The data after an intercurrent event, if collected, will be excluded, observed cases at Week 6 will be included.

2. Multiple imputations: Hypothetical estimand will be used. The data after an intercurrent event discontinuation of study intervention, if collected, will be excluded, observed cases in-person assessment at Week 6 (based on window definition in Table 3) will be included in the analysis. Missing TSS at Week 6 will be imputed using the method of MCMC multiple imputation under MAR assumption. Multiple imputation and subsequent analysis will involve the following four principal tasks:

- 1) Calculate the total number of missing values to be imputed by MCMC (nmiss) for Week 6 value.
- 2) Create a data set, one for each treatment group, of participants with observed values and those needing imputation by MCMC. The missing TSS values in each data set will be filled in using the MCMC method “ $10 \times nmiss$ ” times to generate “ $10 \times nmiss$ ” data sets. The resulting data sets for each treatment group will be combined into one complete data set by imputation. The imputed values will be rounded to the nearest integer of 0 - 12.
- 3) For each complete data set, derive % change from baseline in TSS at Week 6. The estimated treatment effect and its standard error for each complete data set will be calculated using ANOVA ([Section 5.2.1](#)).
- 4) Combine the estimated treatment effects and standard errors from the above into a single inference using Rubin’s formulae as implemented in SAS PROC MIANALYZE.

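### The primary ANOVA of percent change in in-person TSS leaves out a pre-dose baseline that is already collected; prespecify it as a covariate and add an absolute-change sensitivity analysis

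*Protocol*

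**What the plan says.** Protocol 9.4.2 states that the primary endpoint, percent change in TSS scored in person by the home visit practitioner, "will be analyzed using an ANOVA model that includes treatment group as a factor". Protocol 9.4.3 does the same for the secondary area endpoint: "Percentage change from baseline in %BSA at Week 6/EOT based on in-person assessment will be analyzed using an ANOVA model". SAP 6.1.1 and 6.2.6 follow this, and SAP Appendix 1 lists treatment as the only term for both.

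The baseline scores exist. The Schedule of Activities (Protocol 1.3.1) says of TSS, "To be completed by the HVP prior to dose administration at the training visit", and has the same requirement for %BSA. SAP 5.2 defines the value to use: "Baseline value will be the last non-missing assessment on or before Day 1 and prior to first dose of study intervention". SAP 5.2.1 leaves room for adjustment: "ANCOVA will be used if relevant baseline value and/or other factors are included as covariates". No visible analysis of in-person TSS or %BSA takes that option.

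The entry threshold applies at one visit only (Protocol 5.1): "Inadequate response is defined by ISGA ≥ 2 (range 0-4) and TSS ≥ 3 (range 0-12) at the screening visit". SAP 6.1.2 says "Two sensitivity analyses will be performed for the percent change from baseline in the TSS at Week 6 based on HVP in-person assessment". One uses observed cases and the other multiple imputation. Both keep percent change and the treatment-only model.

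For the longitudinal central-reader endpoints, SAP 5.2.1 has a separate rule: "If the endpoint is change from baseline, baseline will be included in the model as a covariate". The corresponding rows of Appendix 1 list treatment, visit and their interaction, with no baseline term.

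**The concern.** There are two distinct points.

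**Unused covariate.** With 35 per arm, the arms can differ in baseline TSS by chance. If baseline is correlated with percent change, part of that imbalance passes into the unadjusted treatment difference. A prespecified covariate corrects for it and multiplies the residual variance by about 1 − rho². It also removes any later choice between adjusted and unadjusted results. Baseline already enters as the divisor, so the relevant rho is that between baseline and percent change, which may well be weak.

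**Small divisors.** Percent change divides by the training-visit score, and the documents set no minimum for that score. Someone who entered with TSS 3 can be rescored at 1 or 2, where a one-point change counts as 100% or 50%. A few such participants can weigh heavily in an arm mean. A linear baseline term does not cure this, and nothing in the visible plan would show whether it had happened.

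**Working it through.** **Inputs.** Protocol 9.2: 35 per arm, difference 22 percentage points, common standard deviation 35, one-sided 5%, power at least 80%. Rho is not in the documents, so a range is shown. Its sign does not matter for power, so absolute values are used.

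**The plan's own figure.** The standard error of the difference is 35 × √(2/35) = 8.37, and the noncentrality is 22/8.37 = 2.63. The noncentral t with 68 df gives power of **83.1%** (83.8% by the normal approximation). The stated figure is reproduced. The 90% CI half-width is 14.0 points.

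**With the baseline covariate.** The residual standard deviation is 35 × √(1 − rho²), with 67 df. Estimating the slope inflates the variance of the difference by about 1 + 1/66. At rho 0.3, for example, the residual standard deviation is 33.4, the standard error is 33.4 × √(2/35) × √(1 + 1/66) = 8.04, and the noncentrality is 22/8.04 = 2.74.

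| Absolute rho | Power | 90% CI half-width |
|---|---|---|
| ANOVA | 83.1% | 14.0 |
| ANCOVA, 0 | 82.6% | 14.1 |
| ANCOVA, 0.12 (break-even) | 83.1% | 14.0 |
| ANCOVA, 0.2 | 83.9% | 13.8 |
| ANCOVA, 0.3 | 85.6% | 13.4 |

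**Chance imbalance.** A baseline imbalance of one standard error shifts the unadjusted difference by 8.37 × rho: 1.7 points at rho 0.2 and 2.5 at rho 0.3, against a target of 22.

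**Plausible rho, by simulation under assumed distributions.** Integer TSS from 0 to 12 was generated, with screening TSS of at least 3 and a baseline re-measured with rater error.

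- *First set:* mean TSS 5 to 7, standard deviation 2, rater-error standard deviation 0.7 to 1.3, 3,000 trials per setting. Eight settings gave a percent-change standard deviation of 33 to 37; a ninth gave 43 and was set aside. Rho ran from −0.11 to −0.32. The covariate changed power by −0.2 to +2.6 points: five settings gave +0.5 or less and three gave 1.8 to 2.6. About 0.5 to 4 of 70 participants had a baseline below 3.
- *Second set:* mean TSS 6, standard deviation 1.8, rater-error standard deviation 0.3 to 1.0, 4,000 trials per setting. Rho ran from −0.04 to −0.21, the power change was −0.1 to +0.9 points, and 0.4 to 1.8 of 70 had a baseline below 3.

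**Leverage of a small divisor (hypothetical).** A 2-point rise from baseline 1 is +200%. Compared with no change, it moves a 35-person arm mean by 200/35 = 5.7 points. The same rise from baseline 6 is +33.3% and moves the mean by 33.3/35 = 1.0 point.

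**The case against.** The strongest reply is that nothing is broken. Randomisation makes the unadjusted ANOVA valid, its power exceeds what Protocol 9.2 promises, and Protocol and SAP agree on the model. Chance imbalance is already reflected in the confidence interval. Rho is unknown, the break-even of 0.12 lies within the simulated range, and most simulated settings show a gain of half a point or less. All of that stands. It limits the size of the claim but does not remove the case for the covariate: the worst case is about half a power point, while the better settings gain 2 to 3 points.

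On small divisors, low baselines would be uncommon, and the 5.7-point example combines a baseline of 1 with a worsening whose frequency is not estimated. Stopping prior treatment for washout might raise scores after screening. Absolute change also estimates a different quantity. These are reasons to make it a sensitivity analysis and nothing more. Such an analysis exists to show whether the rare cases mattered.

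Redacted parts of both documents may contain an absolute-change analysis. Only its absence from the two listed sensitivity analyses is established.

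No figure here concerns %BSA. The recommendation for that endpoint rests on the same reasoning, not on a calculation.

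The MMRM point is weak. SAP 4 names change and percent change separately, but the visible longitudinal continuous endpoints are all percent changes, so the baseline rule is most naturally read as covering them. It needs one clarifying sentence and adds nothing to the main case.

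**Conclusion.** The point holds as an improvement to efficiency and robustness. It is not a validity defect, and the sample size stands without it. Under the Protocol 9.2 assumptions, the covariate changes power by −0.5 points at rho 0, +0.8 at 0.2 (83.9 − 83.1) and +2.5 at 0.3 (85.6 − 83.1). It also corrects the 1.7 to 2.5 points that a one-standard-error baseline imbalance would add at rho 0.2 to 0.3. The gain is probably small, because rho must be assumed and the simulations rest on assumed TSS distributions. The absolute-change analysis is recommended for robustness only, and no power gain is claimed for it. Confidence is medium.

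**What to change.** 1. In Protocol 9.4.2 and 9.4.3 and in SAP 6.1.1, 6.2.6 and Appendix 1, prespecify ANCOVA with treatment and the baseline in-person value of the same measure (TSS or %BSA), using the SAP 5.2 definition of baseline. Keep the treatment-only ANOVA as a supportive analysis.
2. In SAP 6.1.2, add a sensitivity ANCOVA of absolute change in in-person TSS with treatment and baseline TSS, unless the redacted text already holds one.
3. In SAP 5.2.1 and Appendix 1, state whether baseline is a covariate in the percent-change MMRMs.

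No other covariate is proposed.

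The cost is wording, one degree of freedom, and about 0.5 power points if rho is zero. No new data, visits or participants are needed. SAP section 2 says that major changes to the primary analysis are also reflected in a protocol amendment, so item 1 would probably need one. Items 2 and 3 need SAP wording only.

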9.4.3. Secondary Endpoints/Estimands Analysis

Percentage change from baseline in %BSA at Week 6/EOT based on in-person assessment will be analyzed using an ANOVA model that includes treatment group as a factor (see [Section 9.4.1.2](#)) based on Estimand 1 using FAS.

Achievement of an ISGA success and ISGA clear/almost clear at Week 6/EOT based on in-person assessment will be analyzed using the method described in [Section 9.4.1.1](#) using Estimand 1 and FAS.

Percent change from baseline in TSS and %BSA based on Central Readers assessments will be analyzed using MMRM as described in [Section 9.4.1.2](#). Missing data are assumed MAR. Under MAR assumption, MMRM will yield unbiased estimates and valid inferences for treatment effects assuming all participants maintain therapy. This analysis will be based on Estimand 3 using FAS.

Achievement of an ISGA success and ISGA clear/almost clear by time point based on Central Readers assessments will be analyzed using the method described in [Section 9.4.1.1](#). Observations after the discontinuation of study intervention or missing values for any reason will be handled by setting the endpoint to nonresponsive. Note that this is a composite endpoint in the sense that a response requires the participant completes a visit of interest eg, Week 6, and achieves a response per the defined response criteria (otherwise it is considered a nonresponse). This method of handling missing response is known as missing response as non-response (MR-NR). The analysis will be based on Estimand 2 using FAS.

CCI

9.4.5. Safety Analyses

All the safety data will be summarized descriptively through appropriate data tabulations, descriptive statistics, and graphical presentations. All safety analyses will be performed on the safety population as previously defined.

Endpoint	Statistical Analysis Methods
Secondary	Safety Population, Descriptive statistics.

9.5. Interim Analyses

An IA may be performed to assess efficacy and safety after approximately 50 participants complete 6 weeks treatment or early discontinue study intervention. If an IA is performed, IA results will be used for decisions regarding stopping for futility and planning for future studies. There is no efficacy claim and no sample size adjustment based on the IA results.

Participants may be discontinued from the study as a result of the IA, as described in [Section 7](#).

This is an administrative interim analysis; no adjustment of p-values is planned for the analysis of the final study data.

Before the IA is performed, the details of the objectives, decision criteria, dissemination plan, and method of maintaining the study blind as per Pfizer's SOPs will be documented and approved in an IRC charter. In addition, the analysis details will be documented and approved in a SAP. The results of the IA will not be shared with the study team, sites, or participants during the conduct of the study, except in a situation where the IRC recommends early termination of the study.

10. SUPPORTING DOCUMENTATION AND OPERATIONAL CONSIDERATIONS

10.1. Appendix 1: Regulatory, Ethical, and Study Oversight Considerations

10.1.1. Regulatory and Ethical Considerations

- This study will be conducted in accordance with the protocol and with the following:
 - Consensus ethical principles derived from international guidelines including the Declaration of Helsinki and Council for International Organizations of Medical Sciences (CIOMS) International Ethical Guidelines
 - Applicable ICH Good Clinical Practice (GCP) Guidelines
 - Applicable laws and regulations, including applicable privacy laws.
- The protocol, protocol amendments, ICF, Investigator Brochure, and other relevant documents (e.g., advertisements) must be reviewed and approved by the sponsor and submitted to an IRB/IEC by the investigator and reviewed and approved by the IRB/IEC before the study is initiated.
- Any amendments to the protocol will require IRB/IEC approval before implementation of changes made to the study design, except for changes necessary to eliminate an immediate hazard to study participants.
- The investigator will be responsible for the following:
 - Providing written summaries of the status of the study to the IRB/IEC annually or more frequently in accordance with the requirements, policies, and procedures established by the IRB/IEC
 - Notifying the IRB/IEC of SAEs or other significant safety findings as required by IRB/IEC procedures

- Providing oversight of the conduct of the study at the site and adherence to requirements of 21 code of federal regulations (CFR), ICH guidelines, the IRB/IEC, European regulation 536/2014 for clinical studies (if applicable), and all other applicable local regulations
- In the event of any prohibition or restriction imposed (ie, clinical hold) by an applicable regulatory authority in any area of the world, or if the investigator is aware of any new information that might influence the evaluation of the benefits and risks of the study intervention, Pfizer should be informed immediately.
- In addition, the investigator will inform Pfizer immediately of any urgent safety measures taken by the investigator to protect the study participants against any immediate hazard, and of any serious breaches of this protocol or of ICH GCP that the investigator becomes aware of.

